### *4. 18- week adjustment*

At 18 weeks ± 4 weeks, all treatment arm subjects whose balloon has not been removed will be evaluated to determine if an upward adjustment is clinically appropriate. The following algorithm will be followed:

1. Subjects who have reached goal weight (calculated by BMI of 25) **and** are without any symptoms of gastroesophageal reflux or symptoms suggestive of gastritis or gastric ulcer, will not receive a balloon volume adjustment, and endoscopy at 18± 4 weeks will not be performed.
2. Subjects who underwent a prior unscheduled endoscopy with findings of a gastric ulcer will not receive an adjustment at 18± 4 weeks and no additional endoscopy beyond that described in section 2 above will be performed.
3. For all other subjects, endoscopy will be performed, and adjustments/treatment decisions will reflect the following algorithm:
  - a. For subjects with gastric ulceration found at endoscopy, **no upward adjustment** and PI will decide if balloon requires extraction based on endoscopic findings as described below.

Subjects who present with an endoscopically confirmed gastric ulcer will be treated as follows:

- **Ulcers whose smallest dimension (S) is  $\geq 2$ cm, or if there are any stigmata of increased risk of bleeding, such as visible vessels or clots**

The balloon should be extracted. Biopsy for H.pylori will be performed and treatment prescribed if positive.

These subjects should be treated with the following regimen: with sucralfate 1,000 mg PO Qid, and PPI medication twice daily for 3 months, followed by endoscopic evaluation after 3 months to confirm healing.

- **Ulcers whose smallest dimension (S) is  $\geq 1$  cm and  $< 2$  cm**

The balloon volume should be decreased by 150 ml (or 100 ml if starting volume is 400 ml) and subjects should be treated with the following regimen: sucralfate 1,000 mg PO Qid and increasing PPI medication to twice daily for 2 months. A biopsy for H.pylori will be taken and treatment prescribed if positive.

Endoscopic follow up will be performed at 8 weeks and if not healed at 8 weeks, an additional endoscopy at 16 weeks to confirm healing.

- At the 8-week follow-up, if signs of healing defined by a 25% reduction in either length or width are not observed, then the balloon should be extracted.
- At the 16-week follow-up, if signs of healing defined by a 50% reduction from baseline in either length or width are not observed, then the balloon should be extracted, and healing confirmed at follow up endoscopy 2-3 months after extraction.

- **Ulcers whose largest dimension is  $\geq 1$  cm and whose smallest dimension (S) is  $< 1$  cm.**

The balloon volume should be decreased by 150 ml (or 100 ml if starting volume is 400 ml) and subjects should be treated with the following regimen: sucralfate 1,000 mg PO Qid and increasing PPI medication to twice daily for 3 months. A biopsy for H.pylori will be taken and treatment prescribed if positive.

Endoscopic follow up will be performed at 12 weeks and if not healed at 12 weeks, an additional endoscopy at 20 weeks to confirm healing.

- At the 12-week follow-up, if signs of healing defined by a 25% reduction in either length or width are not observed, then the balloon should be extracted.
- At the 20-week follow-up, if signs of healing defined by a 50% reduction from baseline in either length or width are not observed, then the balloon should be extracted.

These recommendations are summarized in the following table:

		L – Largest Dimension (cm)				
		0 – 0.5	0.5 – <1.0	1 – <2	2 – <3	≥ 3
S - Smallest Dimension (cm)	0 – 0.5	Not ulcer	Increase Medication	Decrease balloon volume Follow-up 12 and 20 weeks	Decrease balloon volume Follow-up 12 and 20 weeks	Decrease balloon volume Follow-up 12 and 20 weeks
	0.5 - <1		Increase Medication	Decrease balloon volume Follow-up 12 and 20 weeks	Decrease balloon volume Follow-up 12 and 20 weeks	Decrease balloon volume Follow-up 12 and 20 weeks
	1 - <2			Decrease balloon volume Follow-up 8 and 16 weeks	Decrease balloon volume Follow-up 8 and 16 weeks	Decrease balloon volume Follow-up at 8 and 16 weeks*
	≥ 2				Remove Device	Remove Device*

\*Endoscopically Significant

All subjects in whom a gastric ulcer is confirmed will have endoscopic confirmation of complete healing 2-3 months after the balloon extraction.

Erosive gastritis, and Small Ulcers

Subjects with ulcers < 1 cm in diameter in all dimensions (< 0.5 cm is not considered an ulcer) and erosive gastritis should be treated with the following regimen: sucralfate 1,000 mg PO Qid and increasing PPI medication to twice daily for 3 months. A biopsy for H.pylori will be taken and treatment prescribed if positive. Balloon volume reduction at the discretion of the PI.

Endoscopic follow-up of these subjects prior to the 8-month extraction is not needed if they are asymptomatic.

- b. For subjects with Esophagitis grade 3 or 4, the balloon will be extracted, with the following medication regimen given for 3 months:
  - Increase PPI to BID
  - Add Reglan 10 mg ac and Qhs
  - Add Gaviscon or Maalox 30 ml Q4h
  - Add Sucralfate Suspension 1,000 mg PO QID

Endoscopic evaluation after 3 months to confirm healing.

- c. For subjects with esophagitis grade 1 or 2, no volume addition is given and the balloon may be left in place, with the following medication regimen given for 2-3 months:

- Increase PPI to BID
- Add Reglan 10 mg ac and Qhs
- Add Gaviscon or Maalox 30 ml Q4h prn
- Add Sucralfate Suspension 1,000 mg PO QID

If asymptomatic, endoscopic follow-up deferred until the extraction endoscopy at 8 months.

- d. For subjects with non-erosive gastritis found at endoscopy, balloon volume addition can be performed as per parameters below. These subjects will be treated with increasing PPI medication to twice daily for 2 months. A biopsy for H.pylori will be performed and treatment prescribed if positive. Endoscopic follow up and healing confirmation (and H.pylori eradication, if positive) deferred until the extraction endoscopy at 8 months, unless symptomatic.
4. For subjects without gastric ulceration, erosive gastritis or esophagitis (any grade), the following volume addition parameters should be followed:
- No addition for GE reflux symptoms not controlled by medication
  - 200 ml for subjects who previously received down adjustment for intolerance, but are currently asymptomatic
  - 200 ml for any height with GE reflux symptoms controlled by medication
  - 250 ml for height < 64 inches without GE reflux symptoms
  - 300 ml for height  $\geq$  64 inches without GE reflux symptoms

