## 2. *Unscheduled endoscopy*

An unscheduled endoscopy may be performed at any time at the discretion of the investigator.

The following procedures will be applied to subjects who present with endoscopic findings based on an unscheduled endoscopy.

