These subjects will not undergo adjustment at 18±4 weeks.

These recommendations are summarized in the following table:

		L – Largest Dimension (cm)				
		0 – 0.5	0.5 – <1.0	1 – <2	2 – <3	≥ 3
S - Smallest Dimension (cm)	0 – 0.5	Not ulcer	Increase Medication	Decrease balloon volume Follow-up 12 and 20 weeks	Decrease balloon volume Follow-up 12 and 20 weeks	Decrease balloon volume Follow-up 12 and 20 weeks
	0.5 - <1		Increase Medication	Decrease balloon volume Follow-up 12 and 20 weeks	Decrease balloon volume Follow-up 12 and 20 weeks	Decrease balloon volume Follow-up 12 and 20 weeks
	1 - <2			Decrease balloon volume Follow-up 8 and 16 weeks	Decrease balloon volume Follow-up 8 and 16 weeks	Decrease balloon volume Follow-up at 8 and 16 weeks*
	≥ 2				Remove Device	Remove Device*

\*Endoscopically Significant

All subjects in whom a gastric ulcer is confirmed will have endoscopic confirmation of complete healing 2-3 months after the balloon extraction.

Erosive gastritis, and Small Ulcers

Subjects with ulcers < 1 cm in diameter in all dimensions (< 0.5 cm is not considered an ulcer) and erosive gastritis should be treated with the following regimen: sucralfate 1,000 mg PO Qid and increasing PPI medication to twice daily for 3 months. A biopsy for H.pylori will be taken and treatment prescribed if positive. Balloon volume reduction at the discretion of the PI.

Endoscopic follow-up of these subjects prior to the 8-month extraction is not needed if they are asymptomatic. These subjects will not undergo adjustment at 18±4 weeks.

Non-Erosive Gastritis

If non-erosive gastritis is found at endoscopy, subjects will be treated with increasing PPI medication to twice daily for 2 months. A biopsy for H.pylori will be performed and treatment prescribed if positive.

Endoscopic follow up and healing confirmation (and H.pylori eradication, if positive) will be deferred until the adjustment endoscopy at week 18±4 weeks or extraction endoscopy at 8 months, whichever comes first (must be at least 2 months after this unscheduled endoscopy), unless symptomatic.

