### Esophagitis

Subjects who present with esophagitis will be treated as follows:

- For subjects with esophagitis grade 3 or 4 at endoscopy, the balloon will be extracted, with the following medication regimen given:
  - Increase PPI to BID
  - Add Reglan 10 mg ac and Qhs
  - Add Gaviscon or Maalox 30 ml Q4h prn
  - Add Sucralfate Suspension 1,000 mg PO QID

Endoscopic evaluation will be conducted after 3 months to confirm healing.

- For subjects with esophagitis grade 1 or 2 at endoscopy, the balloon may be left in place, with the following medication regimen given for 2-3 months:
  - Increase PPI to BID
  - Add Reglan 10 mg ac and Qhs
  - Add Gaviscon or Maalox 30 ml Q4h prn
  - Add Sucralfate Suspension 1,000 mg PO QID

Endoscopic follow-up of these subjects prior to the 8-month extraction is not needed if they are asymptomatic. These subjects will not undergo adjustment at 18±4 weeks.

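### The 18-week adjustment algorithm carries forward only a prior gastric ulcer, although the unscheduled-endoscopy rules also bar adjustment after erosive gastritis or grade 1-2 esophagitis

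*Combined protocol and SAP*

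**What the plan says.** All the relevant text is in Section 4.3.3.2.5 (Adjustments) of the combined protocol and SAP.

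- **Item 2, Unscheduled endoscopy.** Such an endoscopy is open at any point: "An unscheduled endoscopy may be performed at any time at the discretion of the investigator". The rules below it are mandatory: "The following procedures will be applied to subjects who present with endoscopic findings based on an unscheduled endoscopy".
- **Item 2, Erosive gastritis and Small Ulcers.** "Endoscopic follow-up of these subjects prior to the 8-month extraction is not needed if they are asymptomatic. These subjects will not undergo adjustment"; the visit meant is the one at 18±4 weeks. Treatment lasts 3 months. On volume: "Balloon volume reduction at the discretion of the PI".
- **Item 2, Esophagitis.** For grades 1 and 2 the balloon may stay in, with 2 to 3 months of medication, and the same bar applies: "These subjects will not undergo adjustment at 18±4 weeks".
- **Item 2, Non-Erosive Gastritis.** There is no bar. Follow-up is "deferred until the adjustment endoscopy at week 18±4 weeks or extraction endoscopy at 8 months, whichever comes first".
- **Item 4, 18-week adjustment, step 2.** "Subjects who underwent a prior unscheduled endoscopy with findings of a gastric ulcer will not receive an adjustment" at that visit.
- **Item 4, step 3.** "For all other subjects, endoscopy will be performed, and adjustments/treatment decisions will reflect the following algorithm".
- **Item 4, step 4.** Subjects without gastric ulceration, erosive gastritis or esophagitis of any grade follow a table of volume additions. Reflux controlled by medication gives 200 ml, as does an earlier reduction for intolerance in a subject now free of symptoms. Without reflux symptoms, the addition is 250 ml below 64 inches and 300 ml at or above. Uncontrolled reflux gives none.
- **Note after step 4.** Subjects who had the early 250 ml addition are to have the 18-week adjustment, limited only by the 1,000 ml maximum.

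**The concern.** Item 2 sets three bars on the 18-week adjustment: after a gastric ulcer, after erosive gastritis, and after grade 1-2 esophagitis. Step 2 of the 18-week algorithm repeats only the first. Section 4.3.3.2.4 defines a gastric ulcer as a lesion of at least 5 mm with unequivocal depth, which covers neither of the other two findings. Because step 3 then takes all remaining subjects, someone working from the 18-week algorithm alone would conclude that the other two bars do not apply there.

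What is at stake is a safety rule. A subject with mucosal injury earlier in balloon treatment could have the balloon enlarged although another operative rule forbids it. The protocol itself treats volume as relevant to injury: ulcers of 1 cm or more in their largest dimension call for a volume reduction or removal, and uncontrolled reflux rules out an addition.

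**Working it through.** **Tracing one subject.** Take a subject with erosive gastritis or grade 1-2 esophagitis at an unscheduled endoscopy, balloon still in place, and the lesion healed by the 18-week visit.

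| Rule | Applies? | Result |
|---|---|---|
| Item 2, erosive gastritis or esophagitis | Yes, whatever the healing | No adjustment; endoscopy before extraction not needed if asymptomatic |
| Item 4, step 1 | Only at goal weight and symptom-free | Otherwise go on |
| Item 4, step 2 | No: the finding was not a gastric ulcer | Go on |
| Item 4, step 3 | Yes | Endoscopy; with a clear result, 3a to 3d give no stop |
| Item 4, step 4 | Yes, unless reflux is uncontrolled | Addition of 200, 250 or 300 ml |

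The first row and the last disagree. If the lesion is still present at 18 weeks, both sets of rules give no addition, so the conflict is confined to healed lesions.

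**Texts that might have settled it but do not.**

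- The step 4 row for earlier intolerance asks only about present symptoms. Adjustments are done by endoscopy (item 5), so each such subject has already had one since implantation, and the row does not ask what it showed.
- The early-addition note names no exception except the maximum volume.
- The visit table in Section 4.3.4 covers only subjects who need no unscheduled endoscopy.

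**Volumes reached under step 4.** The starting fills are 400 or 450 ml (height below 64 inches) and 500 or 550 ml (64 inches or more), from Section 4.3.3.2.1. Intolerance reductions are 100 ml from 400 and 150 ml from the other fills, from item 1.

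| Path | Arithmetic (ml) | Final volume (ml) |
|---|---|---|
| No earlier change | 400 + 200 or 250; 450 + 200 or 250; 500 + 200 or 300; 550 + 200 or 300 | 600 to 850 |
| Intolerance reduction, then 200 | 400→300→500; 450→300→500; 500→350→550; 550→400→600 | 500 to 600 |
| Early 250, then step 4, capped at 1,000 | 650 + 200 or 250; 700 + 200 or 250; 750 + 200 or 300; 800 + 200 or 300 | 850 to 1,000 |
| Early 250, intolerance reduction, then 200 | 650→550→750; 700→550→750; 750→600→800; 800→650→850 | 750 to 850 |

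On the first path the addition runs from 200/550 = 36.4% to 250/400 = 62.5% of the starting fill. On the second it runs from 200/400 = 50.0% to 200/300 = 66.7% of the reduced fill, and the balloon ends 50 to 100 ml above its starting fill. On the third the cap leaves 200 to 250 ml actually added.

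The size of the discretionary reduction for erosive gastritis is not given. Assuming the same 100 or 150 ml as for intolerance, step 4 would end at 500 to 700 ml. Combined with the early addition it could reach 550 + 250 − 150 + 300 = 950 ml.

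**Could treatment finish in time?** Take 3 months as about 13 weeks and 2 months as about 9 weeks, with visits at weeks 14, 18 and 22.

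- A 3-month course is complete if the lesion was found by week 14 − 13 = 1, 18 − 13 = 5 or 22 − 13 = 9.
- A 2-month esophagitis course is complete if it was found by week 14 − 9 = 5, 18 − 9 = 9 or 22 − 9 = 13.

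A completed course does not prove healing, but the case is feasible within the window.

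**The case against.** The strongest reply is that the two items can be read together. Item 2 is specific and mandatory for exactly these subjects, and it names the 18-week adjustment. Item 4 opens by asking whether an increase is clinically appropriate, and Section 7.1.4 calls the volume change optional. Step 4 is limited to subjects without ulceration, erosive gastritis or esophagitis and does not add that the lesion must be found at the 18-week endoscopy. Only steps 3a and 3d use such wording. If being without these lesions includes past ones, step 4 directs no addition. The early-addition note may be meant only to explain the maximum volume. The volumes above are fills the protocol ordinarily permits, not evidence of harm, and a final volume above 900 ml brings a mucosal check at 4 weeks (item 6).

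Much of this stands. A site that follows item 2 is right, and an addition is not inevitable. Three things remain:

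- No text gives item 2 precedence, and repeating one bar of three before sending all others onward points the other way.
- Step 2 refers expressly to a prior finding and step 4 does not, so reading history into step 4 is arguable but not secure.
- Even on the harmonised reading, step 3 requires an endoscopy that item 2 says asymptomatic subjects do not need.

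The item 6 check is not reached where there was no early addition, since those paths end at 850 ml or less.

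**Conclusion.** The point holds. Step 2 is narrower than the bars it should carry forward. Read literally, steps 3 and 4 lead to an addition of up to 300 ml in healed subjects whom item 2 excludes. This assumes that the subject is not at goal weight, has no uncontrolled reflux and has a clear 18-week endoscopy.

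That step 2 is the text to correct is an inference, but a well-supported one. Item 2 sends non-erosive gastritis on to the adjustment endoscopy while barring adjustment after erosive gastritis, so the distinction looks deliberate. Section 4.3.3.2.1 also groups esophagitis, erosive gastritis and ulceration as contraindications at implantation.

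The number of subjects concerned cannot be estimated from the documents. This is an inconsistency in a safety procedure that should be corrected. It has no bearing on the primary analyses, alpha or sample size.

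**What to change.** 1. Extend step 2 so that a prior unscheduled finding of gastric ulcer, erosive gastritis, or esophagitis grade 1 or 2 rules out the 18±4-week adjustment.
2. Keep step 2's present endoscopy wording for gastric ulcer. For the two added findings, state that the 18-week endoscopy is not required in asymptomatic subjects and otherwise remains at the investigator's discretion under item 2.
3. Open the early-addition note with a clause making it subject to steps 1 to 4.

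The cost is one extended step, one added sentence, one clause and a notice to sites. Visits, analyses and sample size do not change.

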**Note: The Maximum final volume of the balloon must not exceed 1,000 ml.**

Subjects who received an additional 250 ml in the first month for lack of any balloon effect will undergo an 18-week adjustment; however, their maximum final volume cannot exceed 1,000 ml. For example, a subject who started with 550 ml and then received 250 ml addition after 2 weeks due to lack of effect, cannot receive more than 200 ml addition at 18 weeks even if they do not have GE reflux symptoms and are  $\geq$  64 inches.

5. *Adjustment procedure*

The balloon adjustment procedure is done with an endoscopy procedure under the same sedation as the implantation procedure.

The adjustment procedure requires the patient to be on the following dietary restrictions:

- 72 hours prior to the procedure: Soft food only, no meat or vegetables in any form.
- 48 hours prior to the procedure: Full liquids only.
- 24 hours prior to the procedure: Clear liquids only.
- 12 hours prior to the procedure: No food or liquids by mouth.

The adjustment procedure is performed under conscious sedation by the anesthetist similar to the implantation procedure. The endoscope is introduced in the usual manner. The capped valve is identified and the suture loop is grasped with a standard rat tooth grasping forceps. The scope and cap are pulled out of the mouth, (the inflation tube stretches and reaches the mouth – see section 5.1) wherein the cap is twisted off and replaced with the extension tube (provided). The extension tube is lowered down the throat into the esophagus followed by the scope. The adjustment commences by utilizing the 3-way stopcock on the proximal end of the extension tube. Following completion of the adjustment, the extension tube is pulled out of the mouth and is replaced by the cap. The cap is lowered back into the throat and allowed to pull itself back to its position touching the white catheter. The scope then pushes it down into the stomach.

#### *6. Follow-up Endoscopy*

All study subjects whose final adjusted volume is >900 ml will receive a follow-up endoscopic mucosal evaluation 4 weeks following the adjustment.

#### **4.3.3.2.6. Extraction**

The extraction procedure requires the patient to be on the following dietary restrictions:

- 72 hours prior to the procedure: Soft food only, no meat or vegetables in any form.
- 48 hours prior to the procedure: Full liquids only.
- 24 hours prior to the procedure: Clear liquids only.
- 12 hours prior to the procedure: No food or liquids by mouth.

The extraction procedure is performed under conscious sedation by the anesthetist similar to the implantation procedure. The endoscope is introduced in the usual manner. The capped valve is identified and the suture loop is grasped with a standard rat tooth grasping forceps. The scope and cap are pulled out of the mouth, wherein the cap is twisted off. A large polypectomy snare is inserted into the biopsy channel of the scope and the snare is opened and placed on the valve. Then the extension tube (provided) is connected to the valve. The scope (with snare closed on the valve) and the extension tube are lowered down the throat into the esophagus. The balloon deflation commences by utilizing the 3-way stopcock on the proximal end of the extension tube. Following completion of the deflation, the scope is pushed down to the gastro-esophageal junction to confirm complete deflation of the balloon. The snare is opened as the extension tube is pulled until the valve exits the mouth- this will bring the distal white catheter and deflated balloon edge into the open snare. The snare is closed. The scope (with snare secured around balloon/white catheter) and the stretched inflation tube are pulled out together with the balloon in tow. The scope is then reinserted to inspect for any mucosal damage.

Following the extraction procedure, all treatment subjects will be followed for an additional 24 weeks.

#### **4.3.3.2.7. Device Failures**

If a balloon deflation or other device failure due to device malfunction or operator error occurs during the implantation or adjustment procedures or follow-up period, the investigator will replace the failed device with a new device unless doing so is not in the best interest of the patient. All device failures will be reported to the Data Monitoring Committee. The number of

device failures and the circumstances under which they occurred will be included in the final Study Report.

#### 4.3.3.2.8. Pancreatitis

New onset abdominal pain (developed after acute accommodative balloon symptoms of balloon placement and adjustment has resolved) suggestive of pancreatitis (epigastric / RUQ in location with or without radiation to the back, persistent (>3 hours in duration), and associated with nausea, vomiting, or new poor PO tolerance justify checking pancreas enzymes (amylase and lipase).

- If pancreas enzymes (amylase and lipase) are > 3X upper limit of normal for institution,
  - o In a systemically ill patient with evidence of moderately severe or severe acute pancreatitis (requiring > 3 days hospitalization, OR evidence of end organ damage [e.g., acute renal failure, respiratory distress, or meeting SIRS (systemic inflammatory response syndrome) criteria for sepsis], OR cross sectional imaging suggestive of severe acute pancreatitis [peripancreatic fluid collections, pancreatic and peripancreatic necrosis (sterile or infected), pseudocyst and walled-off necrosis (sterile or infected)] -- **Balloon removal** and close clinical follow-up of these severely ill patients
  - o In a patient who does not meet the criteria of severe pancreatitis-- **Balloon volume adjustment** with removal of 150 ml (or 100 ml for a 400 ml balloon) and repeat pancreas enzymes 48 hours after adjustment with clinical follow-up.
- If pancreas enzymes (amylase and lipase) are < 3X upper limit of normal for institution,
  - o In a systemically ill patient with evidence of moderately severe or severe acute pancreatitis (requiring > 3 days hospitalization, OR evidence of end organ damage [e.g., acute renal failure, respiratory distress, or meeting SIRS (systemic inflammatory response syndrome) criteria for sepsis], OR cross sectional imaging suggestive of severe acute pancreatitis [peripancreatic fluid collections, pancreatic and peripancreatic necrosis (sterile or infected), pseudocyst and walled-off necrosis (sterile or infected)] -- **Balloon removal** and close clinical follow-up of these severely ill patients
  - o If typical pain persists for > 48-72 hours -- **Balloon volume adjustment** with removal of 150 ml (or 100 ml for a 400 ml balloon) and repeat pancreas enzymes 48 hours after adjustment with clinical follow-up
  - o If pain resolves and within 48-72 hours -- no further action needed clinical follow-up only.

